6.12 Statistical Methods - Microbiome Sub-Study

For **Aim 1, H1a**, the abundance of bacterial taxa will be analyzed at a community level using pairwise distance between samples, and visualized with Principal Coordinates Analysis. That pairwise distance will be the basis for the omnibus tests in all three aims. Prior to the testing of individual taxa, we will conduct a longitudinal MANOVA (Multivariate ANOVA) based on the profile of relative abundances of the gut taxa of interest. P-values from multiple testing procedures will be corrected to control for a specified false discovery rate using the Hochberg method. For **H1b**, we will repeat the omnibus MANOVA test as in H1a using the absolute levels of metabolites, and follow with tests on individual metabolites should the overall test prove significant. Smoking behavior (smoking rate) will be included in the statistical models for Aim 1 as a covariate, because not all participants will have maintained smoking abstinence from TQD through EOT. **Aim 2** will evaluate the impact of post-cessation changes (pre-post changes) in the gut microbiome on dietary intake (kcals, continuous outcome) and smoking cessation (point-prevalence, binary outcome). We will use generalized linear models fitted using Generalized Estimating Equations. We will specify the logistic model for the binary abstinence outcome, and

CONFIDENTIAL

This material is the property of the University of Pennsylvania. Do not disclose or use except as authorized in writing by the study sponsor

Gaussian dietary intake outcome. We will begin the analysis with the effect of the omnibus measure (pre-post distance). Should that prove significant, we will continue on to specific taxa and metabolites. **Aim 3** will explore whether treatment modifies the effect of gut microbiome changes on dietary intake and smoking cessation. We will enter interaction terms (e.g., treatment x microbiome changes) to the models generated for Aim 2. The interactions will be retained if the z-score is significant ($p<0.05$).

7 Risks / Benefits

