This neuroimaging study will aim to examine a sub-set of the randomized clinical trial participants. Functional magnetic resonance imaging (fMRI) can identify mechanisms underlying behavior change beyond self-report and behavioral measures. We will examine neural responses in three parallel pathways including: cognitive control, food cue reactivity, and food reinforcement. As in the parent study, the primary outcomes will be food intake and 7-day point prevalence abstinence at 12 weeks post target quit date. BOLD signal (secondary outcome) will be measured at pre-treatment (week -2) and end of treatment (week 8). Our three aims address: 1) identifying putative brain mechanisms underlying BAS+ (vs. SC) treatment for smoking cessation and PCWG; 2) evaluating the relative contribution of treatment-induced changes in task related brain signal (Food Cue Response, Food Reinforcement/Choice) in prediction of post treatment food intake; and 3) testing whether BAS+ (vs. SC) induced change in neural responses to food cues and food reinforcement is a stronger predictor of food intake among smokers with greater cognitive control. The findings will address *why* BAS+ may be effective in managing PCWG and provide insight into which patients are best supported by this treatment. We also test whether cognitive control processes moderate the influence of BAS+ treatment on food intake.

1.3 *Background- Microbiome Sub-Study*

The Gut Microbiome May Underpin the Substitution of Food for Cigarettes After Smoking Cessation: Converging research suggests that the gut microbiome may play an important role in modulating post-cessation increases in food intake and set the stage for smoking relapse. Gut bacteria and the brain have a bi-directional route of communication through the microbiome-gut-brain (MGB) axis. As such, smoking cessation-induced perturbations in the gut microbiome have the potential to impact the brain as well as behavior. Preliminary research has shown that smoking cessation results in profound changes in gut microbial abundance within 4

CONFIDENTIAL

This material is the property of the University of Pennsylvania. Do not disclose or use except as authorized in writing by the study sponsor

to 8 weeks after quitting smoking (see Aim 1). These smoking cessation-associated changes (e.g., reduced *Bacteroides*, increased *Firmicutes*) are similar to those observed in obesity.

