2.3 Microbiome Sub-Study

Aim 1: To identify earlier (4-weeks post TQD) and persistent (8-weeks post TQD) smoking cessation associated changes in gut microbiome composition and function.

H1a: Smoking cessation will result in decreases in *Prevotella* and *Bacteroides* species from the *Bacteroidetes* phylum, decreases in β - and γ - *Proteobacteria*, increases in *Clostridium* clusters IV and XIV from the *Firmicutes* phylum, and increases in *Bifidobacteria* and HGC bacteria from the *Actinobacteria* phylum.

H1b. We expect to observe decreases in neurotransmitters implicated in reward (dopamine, serotonin, GABA) as well as their precursors (tyrosine, tryptophan, glutamate), and microbial metabolites involved in appetite regulation (indole and propionate).

Aim 2: To evaluate the relationship between post-cessation changes in the gut microbiome, dietary intake, and smoking abstinence.

H2: Greater post-cessation changes in the gut microbiome will predict increased dietary intake and lower smoking abstinence rates 12 weeks post TQD.

[figure not shown]
Aim 3: To explore whether BAS+ (vs. SC) mitigates the effect of gut microbiome changes on dietary intake and smoking abstinence.

H3: Because BAS+ promotes alternative, non-food sources of reinforcement, BAS+ (vs SC) will mitigate the effects of microbiome changes on dietary intake and smoking abstinence 12 weeks post TQD.

3 Study Design

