6.5.5 Microbiome Variables

Participants who are participating in the microbiome sub-study will be instructed to provide stool samples for metagenomic and metabolomic analysis on **Week -2 (Baseline Visit)**, **Week 4 (Mid-Tx 3 Visit)**, and **Week 8 (End of Treatment Visit after completing TN treatment)**. Changes in gut microbiome composition, as determined by metagenomics, will be derived by comparing the relative abundance of bacteria from baseline to weeks 4 and 8. Changes in neuroactive metabolites, as determined by metabolomics, will be derived by comparing levels from baseline to weeks 4 and 8. Although we have hypotheses involving specific metabolites, we chose an untargeted metabolomics approach to enable the identification of other biomarkers of importance.

CONFIDENTIAL

This material is the property of the University of Pennsylvania. Do not disclose or use except as authorized in writing by the study sponsor

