6.9 Sample Size Determination - Microbiome Sub-Study

Hypotheses will be tested at a global 5% Type 1 error rate (alpha) for each family of hypotheses, and we have chosen a completed sample (N=60) that will achieve at least 80% power using 2-sided tests. Our analysis of power is based on “effect size” (standard difference). We will control error in a family-wise manner, adjusting alpha using the Hochberg step up method for the number of tests within each hypothesis family. For **Aim 1**, we examined power using a preliminary longitudinal MANOVA to test for overall significance, and then examined the individual terms by bacteria or metabolite. If we have 12 to 18 taxa in our panel, we have 80% power for the overall test if two taxa make a 0.35-SD shift in abundance in response to smoking cessation. This assumes no within-subject correlation. Imposing a within subject correlation and using the jackknife variance estimate (clustered by subject) increases power. For follow-up testing, we will detect individual effects provided that at least one effect size exceeds ~ 1.3 .

Aim 2 examines whether the changes in the gut microbiome are associated with food intake and smoking abstinence at week 12. As with Aim 1, we will begin with the omnibus test using the multivariate pairwise distance measure (within subject) as a predictor. For the smoking outcome, we have 80% power to detect an odds ratio of 2.0, reflecting approximately a 20% difference resulting from a 1-SD change in pre-post distance. We also have 80% power to detect a correlation of 0.38, reflecting a 400 Kcal change in food intake. **Aim 3** begins with the model in Aim 2, above and explores interacting effects of treatment (BAS+ vs SC) on the relationship between gut microbiome changes, food intake and smoking abstinence. We will test an interaction effect predicting that the effects of gut microbiome changes (pre-post distance) on food intake and smoking abstinence will favor BAS+ versus SC. We have 80% power to detect a difference of 0.68 in the correlation of pre-post distance with food intake (0.68 versus 0), and a ratio of odds ratios (ORR) of 3.15, corresponding to a 25 to 30% greater change in abstinence for the BAS+ subjects.

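### Microbiome Aim 2 has no term for smoking status at the stool sample, so its abstinence test is biased against H2 and could be masked or reversed

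*Combined protocol and SAP*

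**What the plan says.** Section 2.3 sets the causal order. H1a states that "Smoking cessation will result in decreases in" some named taxa and increases in others. H2 then states: "Greater post-cessation changes in the gut microbiome will predict increased dietary intake and lower smoking abstinence rates 12 weeks post TQD". Section 1.3 says of the expected size that "Preliminary research has shown that smoking cessation results in profound changes in gut microbial abundance within" four to eight weeks of quitting, without a figure.

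Section 6.5.5 defines the gut measure, which "will be derived by comparing the relative abundance of bacteria from baseline to weeks 4 and 8". The outcome is later: Section 6.9 says Aim 2 "examines whether the changes in the gut microbiome are associated with food intake and smoking abstinence at week 12".

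Section 6.12 handles smoking in one place: "Smoking behavior (smoking rate) will be included in the statistical models for Aim 1 as a covariate", for the reason that "not all participants will have maintained smoking abstinence from TQD through EOT". For Aim 2 the same section says "We will begin the analysis with the effect of the omnibus measure (pre-post distance", with follow-up of single taxa and metabolites only if that omnibus test is significant. It lists no smoking term. Aim 3 adds treatment interactions to the Aim 2 models. Nothing restricts Aim 2 to people abstinent at the sample, and the text does not say whether the week-4 or the week-8 sample supplies the second time point. Section 6.5.6 lists week-8 abstinence, with week-12 abstinence, as a primary outcome of the sub-study.

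**The concern.** Abstinence at the stool sample is a common cause of both sides of the Aim 2 abstinence model. By H1a it enlarges the gut change, and it strongly predicts abstinence a few weeks later. Left out, it induces a positive association between distance and week-12 abstinence, while H2 predicts a negative one. The plan recognised the mixture of quitters and continuing smokers and acted on it for Aim 1 only, although the reason it gives applies at least as strongly where abstinence is the outcome.

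Three things are at stake. A real H2 effect could be cancelled, and because the omnibus test is the gate, the single-taxon and metabolite tests for that outcome would then not be run. An association with no gut effect behind it could be declared significant. And Aim 3 inherits the same models. For diet, if quitting raises intake, the omission pushes towards H2 instead.

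**Working it through.** **The plan's own figure.** Section 6.9 claims 80% power at N=60, two-sided, for an odds ratio of 2.0 per SD of distance, with no base rate and no covariate. For a logistic model with one continuous predictor, power = Φ(√(N·p(1−p))·ln OR − 1.96). At p = 0.25 this is Φ(√11.25 × 0.693 − 1.96) = 64%; at p = 0.30, 0.40 and 0.50 it is 69%, 75% and 77%. The 80% is not reproduced even unadjusted. That is a separate matter on which this point does not depend.

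**Assumed inputs (not in the documents).** 35% abstinent at the sample; 70% of these and 7% of the others abstinent at week 12. Abstinence raises the distance by s within-group SDs.

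**Crude odds ratio with no gut effect.** Week-12 abstinence overall is 0.35×0.70 + 0.65×0.07 = 0.2905. The proportion who were abstinent at the sample is 0.245/0.2905 = 0.843 among week-12 abstainers and 0.105/0.7095 = 0.148 among the rest, a difference of 0.695. The two outcome groups therefore differ by 0.695·s in mean distance. The total variance of distance is 1 + 0.35×0.65·s² = 1 + 0.2275s², and the variance within outcome groups is about 1 + 0.128s². So

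ln OR per SD ≈ 0.695·s·√(1 + 0.2275s²)/(1 + 0.128s²).

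For s = 1.0: 0.695 × 1.108/1.128 = 0.683, OR 1.98. Simulation with 400,000 subjects agrees and supplies the column for a true OR of 0.5.

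| Shift s (SD) | Crude OR, no gut effect | Crude OR, true OR 0.5 |
|---|---|---|
| 0.05 | 1.04 | about 0.7 |
| 0.2 | 1.15 | about 0.8 |
| 0.35 | 1.27 | 0.8-0.9 |
| 0.7 | 1.62 | 1.0-1.1 |
| 1.0 | 1.98 | 1.1-1.3 |

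With status at the sample in the model, the odds ratio returns to 1.0 or 0.5 within 0.01. In the last column, the move from 0.5 to about 0.7 at the smallest shift is mostly non-collapsibility of the odds ratio, not confounding; the no-effect column is free of that.

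**At N=60** (1,500 runs per cell; 35% abstinent; week-12 abstinence 65-75% if abstinent at the sample, 5-10% if not). With no gut effect, the crude test is significant above 1 in 27-41% of runs at s = 0.7 and 46-66% at s = 1.0. With a true OR of 0.5 and s = 1.0, the crude estimate exceeds 1 in 62-90% of runs, is significant in the wrong direction in 5-22%, and in the predicted direction in 1% or less.

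**How large might s be?** Section 6.9 powers Aim 1 on two of 12 to 18 taxa moving 0.35 SD. In a Euclidean distance over independent taxa, that shifts the distance by only about 0.05 SD. All eight groups named in H1a moving 0.35 SD give 0.16-0.20. All eight moving 0.7-1.0 SD give about 0.6-1.4.

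**Diet.** Section 6.9 equates r = 0.38 with 400 kcal, so the intake SD is about 400/0.38 = 1,053 kcal. If abstinence raises intake by Δ, the spurious correlation is 0.2275·s·Δ/(√(1 + 0.2275s²) × 1,053). For s = 1.0 and Δ = 400 this is 91/(1.108 × 1,053) = 0.08. Over s = 0.35-1.3 and Δ = 200-400 kcal it is about 0.02-0.10, in the direction of H2.

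**Power after adjustment.** At N=60 and OR 0.5, simulated power is about 32-48%. As a check, the outcome variance left within status groups is 0.35×0.21 + 0.65×0.0651 = 0.116, and Φ(√(60 × 0.116) × 0.693 − 1.96) = 45%.

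**The case against.** The strongest objection is that the size of the shift is nowhere in the documents. The 0.35 SD in Section 6.9 belongs to two taxa, not to the distance, and on that scenario the shift in distance is about 0.05 SD and the bias is negligible. The distance metric is unspecified, and the word profound in Section 1.3 has no number behind it. This stands. A reader might infer that the abstinence result will come out with the wrong sign; the documents do not support that.

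A reader might also infer that the diet half of H2 is likely to be falsely supported. A sizeable error rate there needs abstainers to eat something like 0.8 SD more, which is 0.8 × 1,053 = 842 kcal a day on the sub-study's figures, about twice the 400 kcal it is powered for. At 200-400 kcal the spurious correlation is small.

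A third tempting step is to adjust everything for week-8 abstinence and week-8 intake. That over-adjusts. Both come after the week-4 change. In a simulation where week-4 gut change caused relapse by week 8, conditioning on week-8 abstinence gave an odds ratio of 1.00, while conditioning on week-4 abstinence kept the effect at about 0.7. Section 6.5.6 also places the week-8 recalls in the week after, or near, the visit, so they may post-date the sample.

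It can be said too that Aim 2 speaks of a relationship and an association in a small supplementary study, and that the parent trial's primary outcomes are untouched. Both are true, but H2 is directional and rests on a mechanism, and the crude model cannot address it. The general covariate clause in Section 6.10 covers the parent study; Section 6.12 does not bring it in.

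**Conclusion.** The omission is real and the direction of the bias follows from H1a: the unadjusted abstinence association is biased against H2. Under the assumed abstinence rates the bias is slight for shifts of 0.05-0.2 SD. At about 0.7-1.0 SD it is enough to mask or reverse a true odds ratio of 0.5, and at 1.0 SD confounding alone produces an odds ratio near the 2.0 that Section 6.9 says the sub-study can detect. Which of these applies cannot be settled from the documents, so masking or reversal is a possibility and not a demonstrated result. The diet bias is minor and favours H2. The correction uses data already collected and should be made, with the loss of power stated openly.

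**What to change.** In Section 6.12, add to the Aim 2 and Aim 3 models smoking status at the stool sample that defines the change: week-4 status for baseline-to-week-4 change and week-8 status for baseline-to-week-8 change. Use verified abstinence or the timeline follow-back rate. Section 6.5.2 schedules urine cotinine at week 8 but not at week 4, so week-4 status would rest on follow-back wherever CO was not taken. State which sample is used in each model.

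Report the unadjusted association as descriptive, and show the estimate among those abstinent at that sample as a sensitivity analysis. Do not condition week-4 change on week-8 abstinence. For diet, adjust for baseline intake and smoking status at the sample; use week-8 intake at most in a sensitivity analysis. State that week-8 abstinence, listed as an outcome in Section 6.5.6, is a covariate only in the week-12 models that use the week-8 sample.

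The cost is wording and one or two covariates, with no new data. The real price is precision: about 32-48% power at an odds ratio of 0.5 with N=60 under the assumed rates. The Aim 2 power statement in Section 6.9 should be restated for the adjusted model, with its base rate.

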3.3 General Design - Microbiome Sub-Study

We will study a subsample of up to 60 consecutively recruited smokers enrolled in the parent trial. The microbiome study subgroups will be balanced for age, sex, and BMI. In addition to the exclusion criteria for the parent trial, we will exclude individuals with current and recent (last 3 weeks) use of non-topical antibiotics, antifungals, antivirals, and psychotropic drugs. Participants who are initially eligible based on telephone screening will complete an in-person Intake session as part of the parent study. Before or during the Intake session, consent for participation in the sub-study will be obtained and final sub-study eligibility will be confirmed. An equal number of microbiome eligible smokers from the BAS+ or SC treatment groups will be instructed to provide a stool sample on **Week -2 (Baseline Visit)**, **Week 4 (Mid-Tx 3 Visit)**, and **Week 8 (End of Treatment Visit after completing TN treatment)**. Participants will be instructed to collect a stool sample within 24 hours (up to ~36 hours is permissible) of the target time points. Directions and supplies for stool specimen collection will be provided at the visit prior to collection.

We will assess within-subjects changes in the gut microbiome across time and explore between treatment group comparisons at week 12. As part of the main study, smoking is assessed by self-report and is biochemically confirmed (CO < 5) weekly after quitting, at EOT (week 8), and at the 12- week follow-up. Food intake is measured by three consecutive days of 24-hour food recalls at baseline and 4- 8- 12- week post-TQD.

CONFIDENTIAL

This material is the property of the University of Pennsylvania. Do not disclose or use except as authorized in writing by the study sponsor

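### Microbiome Aim 3: section 6.12 keeps each interaction at p<0.05 with no adjustment stated, although section 6.9 promises a Hochberg-adjusted 5% error rate per hypothesis family

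*Combined protocol and SAP*

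**What the plan says.** Section 6.9 (Sample Size Determination - Microbiome Sub-Study) sets the error policy for the whole sub-study: "Hypotheses will be tested at a global 5% Type 1 error rate (alpha) for each family of hypotheses". The method is family-wise control, "adjusting alpha using the Hochberg step up method for the number of tests within each hypothesis family". No aim is exempted. For Aim 3 the section defines the microbiome change as the pre-post distance and gives power for its interaction with treatment on two outcomes. For food intake: "We have 80% power to detect a difference of 0.68 in the correlation of pre-post distance with food intake (0.68 versus 0"). For abstinence: "a ratio of odds ratios (ORR) of 3.15".

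Section 6.12 (Statistical Methods - Microbiome Sub-Study) adds the treatment interactions to the Aim 2 models and gives one decision rule for them: "The interactions will be retained if the z-score is significant ($p<0.05"). No adjustment is mentioned there. The only multiplicity sentence in 6.12 stands in the Aim 1 text, and it describes Hochberg as a way to control the false discovery rate.

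Section 2.3 gives Aim 3 a directional hypothesis, H3, that names both dietary intake and abstinence. Neither 6.9 nor 6.12 says which tests make up the Aim 3 family.

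**The concern.** The section on error control promises one property, and the only Aim 3 rule in the methods section does not deliver it on its face. With two interactions each judged at .05, the chance of at least one false positive is close to twice the promised 5%.

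H3 is the sub-study's only hypothesis that compares BAS+ with SC, so any statement that the intervention changes the effect of the gut microbiome rests on these tests. If one interaction falls just under .05 and the other does not, an analyst following 6.12 keeps it, and an analyst following 6.9 does not. Unless the text is settled before analysis, the rule can be chosen after the p-values are known.

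**Working it through.** **Inputs.** From section 6.9: 60 completers, two-sided tests, 80% power, correlation 0.68 versus 0, ratio of odds ratios 3.15. From section 3.3: equal numbers per arm, hence 30 each. Assumed: the Aim 3 family is the two interactions powered in 6.9, and the correlation between the two test statistics is 0 to 0.5 (the documents give none).

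**1. The plan's own power figure.** Comparing two correlations by Fisher z:

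- atanh(0.68) = 0.829; standard error = √(2/27) = 0.272; ratio = 3.046.
- Two-sided .05: Φ(3.046 − 1.960) = 86.1%.
- Two-sided .025: Φ(3.046 − 2.241) = 79.0%.

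On that test the stated 80% is reproduced at .025. But 6.12 specifies the z-score of an interaction term in a regression model. Simulating a pooled-variance regression interaction (30 per arm, correlations 0.68 and 0, equal outcome variance, 100,000 runs) gives 80% to 82% at .05 and 72% to 74% at .025, depending on whether a t or a normal critical value is used. On that test the 80% fits .05.

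The abstinence figure does not settle it. With Φ(ln 3.15 / √(2/(30·p(1−p))) − z) and an assumed abstinence rate p of 13% to 50%, power is 32% to 60% at .05 and 23% to 49% at .025, so 80% is reached at neither level. The power figures therefore do not show which alpha was used, and nothing below relies on them.

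**2. Family-wise error under each rule, no true interaction.** With two tests, Hochberg rejects both if the larger p is at most .05. Otherwise it rejects the smaller if that is at most .025. For independent tests:

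- 6.12 rule: 1 − 0.95² = 9.75%.
- Hochberg: 0.05² + 2 × 0.025 × 0.95 = 0.25% + 4.75% = 5.0%.
- Rules disagree: 2 × 0.025 × 0.95 = 4.75%.

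For correlated tests, by simulation (2,000,000 draws):

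| Correlation | 6.12 rule | Hochberg | Rules disagree |
|---|---|---|---|
| 0.3 | 9.5% | 4.9% | 4.6% |
| 0.5 | 9.1% | 4.8% | 4.3% |

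**3. Where the rules part.** They differ only when the smaller p is between .025 and .05 and the other is .05 or more. If both are below .05, Hochberg keeps both, as 6.12 does. If the smaller is below .025, both rules keep it.

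**The case against.** The strongest reply is that Aim 3 is exploratory and 6.12 treats it so. Sections 1.3, 2.3, 3.3, 6.9 and 6.12 all speak of exploring the treatment comparison. Retaining a term is model-building language, and section 6.10 uses the same sentence for the parent study's exploratory moderators. The absence of adjustment is inferred from silence: p<0.05 could be meant as a Hochberg-adjusted p-value, in which case the sections agree. And if each outcome were its own family of one test, no adjustment would be due.

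Part of this stands. The text does not prove that an unadjusted rule was intended, and exempting Aim 3 would be a legitimate choice. But 6.9 covers every family and makes no exception. Section 6.7 does state p<.05 for the parent study's exploratory tests; 6.9 has no such line for Aim 3. In section 6.8 the neuroimaging Aim 3 interactions are Hochberg-adjusted. H3 is one hypothesis naming both outcomes, so treating its two tests as a family is the natural reading.

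Three stronger readings are tempting, and the documents do not support them:

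- A reader might infer from the 80% figure that the sponsor planned Aim 3 at about .025. That holds for a Fisher z comparison but not for the interaction test that 6.12 names.
- A reader might infer that taxon- and metabolite-level interactions multiply the tests and push the error rate far higher. Section 6.9 defines Aim 3 on the pre-post distance for two outcomes; the specific models belong to Aim 2 and follow only a significant omnibus effect. Any larger count would be invented.
- A reader might infer that any p between .025 and .05 is decided two ways. That is so only when the other p is .05 or more.

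**Conclusion.** The point holds as a conflict between the stated error rate and the stated decision rule. Read as written, 6.12 gives a family-wise error of about 9% to 10% for Aim 3 where 6.9 promises 5%, and the two rules reach different conclusions in about 4.3% to 4.75% of trials with no true interaction. These figures assume a two-test family, a correlation of 0 to 0.5 between the tests, and that p<0.05 in 6.12 means an unadjusted p-value. The consequence is confined to the sub-study's one between-arm hypothesis. It is worth settling before analysis.

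**What to change.** In section 6.12, define the Aim 3 family as the two omnibus interactions (pre-post distance by arm, for kcal and for abstinence) and apply Hochberg at 5% across them in place of the per-test p<0.05. State that any taxon- or metabolite-level interaction is reported with estimates and confidence intervals and without a significance claim.

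If the sponsor wants Aim 3 to be unadjusted exploration, say so in section 6.9 as an explicit exemption, and report H3 as exploratory.

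The cost is wording plus a slightly stricter threshold when only one interaction is significant. For the food-intake interaction at the planned effect, the loss of power is at most the gap between testing at .05 and at .025. By the calculations above that is 7 points with Fisher z (86.1% − 79.0%) and 8 to 9 points with the regression test.
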